5.5.1.2 Reason for Discontinued

A study subject will be discontinued from the study if the Investigator is unable to insert a punctal plug in to the study subject's lower punctum, they have experienced a complication (intra-operative exclusion criteria) during surgery, the punctal plug has been extruded after the surgical visit (Visit3), study subject has used a prohibited concomitant therapy, is non-compliant, has missed scheduled study visits, has personal reasons, has relocated out of the area or has a desired to withdraw from further participation in the study in the absence of a medical need as determined by the Investigator. Other reason – the study subject was discontinued for a reason other than those listed above, the Investigator must specify the reason

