6.1.4 Starting Dose

One (1) to 2 days prior to their scheduled cataract surgery, a subject will be randomized (2:1) in to one of two treatment groups. The assigned punctal plug will be inserted in their lower punctum of their scheduled surgical eye.

NOTE: All systemic, topical and ophthalmic NSAIDs or corticosteroid medications, with the exception of a subject who has been prescribed and has been taking a baby aspirin (≤ 81 mg/daily), must be discontinued at least 48 hours prior to the insertion of the punctal plug.

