6.1.7 Unable to Insert/Extruded/Lost Masked Punctal Plug

6.1.7.1 Unable to insert masked punctal plug

If the plug cannot be inserted after a few attempts with gentle dilation, the subject will not be eligible for the study. Lubricants are not to be used.

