10.4 Description of Statistical Methods

10.4.1 General Approach

All statistical tests will be two-sided and interpreted at a 5% significance level. Descriptive statistics (i.e., mean, standard deviation, etc.) will be provided for all continuous variables and frequency distributions will be generated for all categorical variables collected in this study.

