10.4.4 Safety Analyses

All study subjects who are exposed or deemed exposed to study medication will be evaluable for safety analysis. A subject is deemed exposed to study medication if they discontinue the study prior to surgery visit and were implanted with a masked PPDS.

The safety endpoints in this study are adverse events, visual acuity, slit-lamp parameters (Lid, conjunctiva, cornea), fundus findings, and use of rescue medication. Safety variables will be summarized using descriptive statistics.

The type, severity, duration and frequency of reported adverse events will be tabulated for each treatment group, by visit. Adverse events will also be summarized for events and a comparison of the proportion of study patients reporting adverse events between groups will be made using a chi-square test. Additionally, any adverse event experienced by a subject after signing informed consent and before exposure will be presented separately in the safety analysis.

Adverse events will be coded using the Medical Dictionary for Regulatory Activities (MedDRA). Treatment emergent AEs (those occurring after insertion of a study PPDS) will be summarized descriptively: The number and percentage of study subjects who experienced an AE and the total number of AEs will be summarized by system organ class and preferred term. Associated AEs, defined as AEs suspected to be treatment related by the investigator, SAEs and serious associated AEs will also be summarized, if necessary. Summaries of each type of event will be prepared by severity and for all severities combined.

Concomitant medication recorded and used during the study will be coded using the World Health Organization Drug Dictionary and listed by subject. Ocular concomitant medications will be identified by each eye in the listing.

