10.5 Sample Size

Since this is a pilot study, no formal sample size estimation was performed.

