10.6.1 Enrollment/ Randomization/Masking Procedures

Randomization will be stratified (or balanced) by study center. Patients will be randomized in a ratio of 2:1, 2 active (N-PPDS) for each placebo (p-PPDS). Treatment assignments for this study have been randomized in blocks of three (each sequential group of three, two lines are active treatment, and one line is placebo treatment), 25 blocks total. Using a random number generator (JMP 10.0 statistical software), each block is assigned three randomized numbers. The dataset is then sorted by ascending order by block, by random number. By ascending order, each line is assigned a subject number (e.g. 101-175). As a subject qualifies for enrollment, they will be sequentially assigned a subject number. The subject numbers designated what treatment group the subject will be assigned.

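### Treatment-emergent adverse events are counted only after plug insertion, so injuries from the Visit 2 dilation or a failed insertion miss the main adverse event summaries, and insertion success is not tabulated

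*Combined protocol and SAP*

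**What the plan says.** Treatment is assigned before the plug is tried. Section 6.1.4 has the order: "a subject will be randomized (2:1) in to one of two treatment groups. The assigned punctal plug will be inserted". Sections 7.4.2 and 10.6.1 agree, because the subject number given at qualification fixes the arm and the assigned plug is then inserted at Visit 2.

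A failed insertion has two dispositions. Section 6.1.7.1: "If the plug cannot be inserted after a few attempts with gentle dilation, the subject will not be eligible for the study". Section 5.5.1.2: "A study subject will be discontinued from the study if the Investigator is unable to insert a punctal plug". Under Section 5.5.2.2 discontinued subjects are replaced.

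Section 10.4.4 sets the safety rules:

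- The safety set is everyone exposed or deemed exposed. Only the second term is explained: "A subject is deemed exposed to study medication if they discontinue the study prior to surgery visit and were implanted with a masked PPDS".
- On the main event summaries: "Treatment emergent AEs (those occurring after insertion of a study PPDS) will be summarized descriptively". The summaries by system organ class and preferred term, the treatment-related and serious subsets, and the severity breakdown follow from there.
- Events arising between consent and exposure get their own presentation within the safety analysis.
- A further table gives reported events by treatment group and visit, and is not expressly limited to treatment-emergent events.

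No section plans a count of insertion attempts, successes or failures. Section 10.4.5 (adherence and retention) is marked not applicable.

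**The concern.** For a drug-eluting punctal plug, putting it in is part of the treatment and one of its hazards, and the protocol treats it so. Section 6.1.5 allows prolonged and forceful dilation of small puncta. Section 6.1.6 has partly inserted plugs taken out and the punctum dilated again. Section 6.1.9 notes that these plugs are larger than marketed silicone ones, and the gauge instructions in Appendix 1 warn about perforating the punctal ring.

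The clock for the principal adverse event summaries starts after that step. An injury with onset during dilation or a failed push is not treatment-emergent, whether or not a plug is later placed. If none is placed, the subject is also not clearly in the safety set. At stake is whether a reader of the main safety tables can see how often insertion failed and how often it did harm.

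**Working it through.** **1. The plan's own figure.** Section 10.6.1 describes 25 blocks of three: 25 × 3 = 75 numbers, split 50:25. The example range agrees: 175 − 101 + 1 = 75. The list as described therefore has no spare numbers for replacements. There is no failure or injury rate to reproduce, and on sample size Section 10.5 says only: "Since this is a pilot study, no formal sample size estimation was performed".

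**2. Where a pre-insertion injury is counted under Section 10.4.4.**

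| Subject | Safety set | Treatment-emergent summaries | Pre-exposure presentation |
|---|---|---|---|
| Injured in dilation, then implanted | Yes | No | Yes |
| Injured, insertion failed | Not on a literal reading | No | Apparently yes, though this subject is never exposed |
| Insertion failed, no injury | Not on a literal reading | Nothing to count | Nothing to count |

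This takes onset to be recorded as the time of dilation or attempt. An injury noticed only once the plug is in place could be dated either way.

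**3. Number of failed insertions.** Let f be the failure rate, assumed between 1% and 15%. If failures are replaced until 75 subjects are implanted, the number randomised is 75/(1 − f), rounded up. The chance of at least one failure in the first 75 attempts is 1 − (1 − f)^75.

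| f (assumed) | Randomised | Failed | Failed/randomised | Chance of at least one in 75 |
|---|---|---|---|---|
| 1% | 76 | 1 | 1.3% | 53% |
| 2% | 77 | 2 | 2.6% | 78% |
| 5% | 79 | 4 | 5.1% | 98% |
| 10% | 84 | 9 | 10.7% | >99% |
| 15% | 89 | 14 | 15.7% | >99% |

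**4. Where the injuries would lie.** Let d1 be the injury rate in implanted subjects and d2 the rate in failed insertions, both assumed. Expected injuries are 75 × d1 and F × d2, with F = 75/(1 − f) − 75.

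| f | d1, d2 | Implanted | Failed insertions | Share in failed insertions |
|---|---|---|---|---|
| 2% | 2%, 10% | 1.50 | 1.53 × 0.10 = 0.15 | 9% |
| 5% | 5%, 20% | 3.75 | 3.95 × 0.20 = 0.79 | 17% |
| 10% | 5%, 50% | 3.75 | 8.33 × 0.50 = 4.17 | 53% |

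Whatever the rates, none of these events is treatment-emergent as defined. In the first two rows most are in subjects who stay in the safety set, so the start of the clock matters more than the boundary of the set. In the third row the two matter about equally.

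**The case against.** The strongest reply is that nothing is lost. Section 8.7 requires events to be documented from Visit 2, Section 4.2.3 counts events after randomisation, and Section 10.4.4 presents pre-exposure events separately. Its table by group and visit may include them too. The exit form records why a subject left, so failures can be counted afterwards. Starting the clock at treatment is also a common convention. All of this stands, and it limits the point to how events are classified and to a tabulation that is missing.

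It does not remove the point. The pre-exposure presentation has no denominator of attempted insertions. It is not said to carry the coding, severity and relatedness breakdown. Its meaning for a subject who is never exposed is unclear. No planned analysis uses the exit reason.

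Three stronger readings are tempting, and the documents do not support them:

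- **Device failure and harm rates are understated.** No failure rate is planned, so it is unreported rather than understated. Injuries are reported, but apart from the main summaries.
- **The ITT definition hides harm.** It requires a post-operative visit and so excludes failed insertions, but it governs the efficacy analyses.
- **Randomisation should wait for proof of fit.** The plug is pre-loaded and treatment-specific, so insertion cannot be tried before assignment. Dilatability to 1.0 mm is already an entry criterion, and assigning at that moment would intrude on a timed step.

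It is also fair to say that exclusion from the safety set is not certain. Exposed is undefined, and a plug partly inserted and then removed could be argued either way.

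**Conclusion.** The point holds in limited form. As written, injuries from dilation or failed insertion are outside every treatment-emergent summary. Randomised subjects with a failed insertion are outside the safety set on a literal reading, and insertion success is not a planned result. Sections 6.1.7.1 and 5.5.1.2 contradict each other on the same event.

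The size cannot be fixed from the documents. Over the assumed 1% to 15% failure range, 1 to 14 randomised subjects are affected, and the injury figures rest wholly on assumption. The plug body and excipients are the same in both masked arms (Section 6.1.2 and Appendix 6), so failures and insertion injuries should be similar by arm. The consequence is for absolute device rates, and no bias in the treatment comparison is shown. This is an inexpensive improvement that should be made, but it is not a flaw that invalidates the safety analysis.

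**What to change.** - **Section 10.4.4, safety set:** all randomised subjects in whom punctal dilation or plug insertion was attempted at Visit 2.
- **Section 10.4.4, treatment-emergent events:** those with onset from the start of that Visit 2 procedure.
- **New tabulation:** insertion attempts and failures by arm, over all randomised subjects.
- **Sections 6.1.7.1 and 5.5.1.2:** reconcile the disposition of a failed insertion, and with it the replacement rule in Section 5.5.2.2. The safety-set wording above works whichever disposition is chosen.

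The cost is wording and one CRF field for attempts. The stated adverse event rate may rise slightly. Adding subjects who received no drug also enlarges the denominator: at an assumed 5% failure rate, from 75 to 79, which multiplies a rate seen only in implanted subjects by 75/79 = 0.95. Showing the implanted subset alongside would deal with that.

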10.4.5 Adherence and Retention Analyses

N/A

10.4.6 Baseline Descriptive Statistics

Demographic and baseline characteristics will be summarized by treatment group and overall. Counts and percentages will be presented for categorical variables such as sex, age group (by decade), race, ethnicity, cataract density and type. Mean, standard deviation, median, minimum and maximum will be presented for continuous variables such as age, punctum size (non-dilated) and visual acuity scores.

10.4.7 Planned Interim Analyses

An interim analysis will be performed to confirm that positive efficacy trends are being observed and that the enrolment should continue. The interim analysis will be performed after a minimum of 25 subjects have completed visit 7 in the study. The data will be unmasked and analysis of primary and secondary endpoints will be completed along with baseline descriptive statistics.

Sites will remain masked to treatment for the remainder of the study. A summary of the results may be shared with the sites but no individual site data will be generated or shared.

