4.2 Study Endpoints

The study will be complete when 75 study subjects (75 eyes) have been evaluated at Visit 7 (Day 14 post-op) or have been terminated from the study.

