4.2.1 Primary Efficacy Endpoint

The primary effectiveness endpoint will analyze the Investigator's evaluation of study subject's ocular pain following cataract surgery compared with placebo at 1, 3, 7 and 14 days post-op.

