8.8 Study Halting Rules

Collaboration between representatives of Mati Therapeutics Inc., Investigators and statisticians may stop the study if there is evidence of a lack of safety or efficacy associated with the study drug/device or if there is sufficient evidence of efficacy to warrant phase III testing.

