10.6 Measures to Minimize Bias

To minimize bias, the study has been designed as a randomized, double blind study.

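### Section 10.4.7 permits a summary of unmasked interim efficacy results to go to the sites, and Section 8.8 gives Investigators a part in efficacy stopping, although the same Investigators rate pain, cells and flare in the remaining subjects.

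*Combined protocol and SAP*

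**What the plan says.** Section 10.4.7 plans one interim analysis, to confirm positive efficacy trends and decide whether enrolment should go on. It takes place after a minimum of 25 Visit 7 completers; no maximum is set. The data are unmasked and both efficacy endpoints are analysed. Sites stay masked to treatment, but: "A summary of the results may be shared with the sites but no individual site data will be generated or shared". What the summary would contain is not defined.

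Section 8.8 gives the stopping decision to sponsor representatives together with others: "Investigators and statisticians may stop the study if there is evidence of a lack of safety or efficacy". The same sentence allows stopping when efficacy is strong enough to justify Phase III.

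On who produces the data, Section 4.2.1 states: "The primary effectiveness endpoint will analyze the Investigator's evaluation of study subject's ocular pain following cataract surgery compared with placebo". Section 7.2.1 has the Investigator interview the subject and record the answer, and says that the person who does this on Day 1 should do it at every later post-op visit. The same request applies to the slit-lamp examination. Appendix 2 has the Investigator grade cells and flare.

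On bias control, Section 10.6 states: "To minimize bias, the study has been designed as a randomized, double blind study". Section 10.6.2 plans no evaluation of masking success. Section 8.9 names a masked Medical Monitor. No section sets up an independent committee or a barrier around the interim results.

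**The concern.** The statement that sites remain masked covers each subject's assignment. It does not cover the aggregate answer to which arm is doing better, and that answer is what Section 10.4.7 allows to be sent out. Section 8.8 opens a second possible route, because a person who helps to decide on stopping for efficacy would be expected to see efficacy evidence.

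Knowledge of the effect could enter the trial in three ways:

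- **Scoring.** Pain is reported by the subject but elicited and graded by the Investigator. Flare grades rest on appearance. Expectation can affect both.
- **Guessing.** A rater who knows the effect can use a subject's Day 1 state as a clue to the arm. If the same person rates Days 3, 7 and 14, the clue carries forward. Section 10.6.1 adds to this: "Treatment assignments for this study have been randomized in blocks of three". A confident guess about one subject therefore says something about the next subjects at that site.
- **Which data exist.** Termination for moderate to severe pain or inflammation rests on the Investigator's judgment (Section 5.5.1.1). Rescue involves discretion once a criterion is met (Section 7.9.1). The efficacy analysis uses observed data only (Section 10.4.3).

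At stake is the credibility of the masked comparison on the primary endpoint in subjects rated after disclosure.

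**Working it through.** **1. The plan's own figure.** Section 10.6.1 gives 25 blocks of three at 2:1. 25 × 3 = 75, made up of 25 × 2 = 50 active and 25 × 1 = 25 placebo. This agrees with Section 4.2: "The study will be complete when 75 study subjects (75 eyes) have been evaluated at Visit 7 (Day 14 post-op) or have been terminated". There is no power calculation to reproduce: "Since this is a pilot study, no formal sample size estimation was performed".

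**2. Subjects not yet completed at the interim.** Formula: (75 − completers)/75.

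| Completers at interim | Not yet completed | Share |
|---|---|---|
| 25 (the minimum) | 50 | 67% |
| 30 | 45 | 60% |
| 40 | 35 | 47% |
| 50 | 25 | 33% |

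These are ceilings, because some of these subjects are already in follow-up. Assume even accrual over 20 to 26 weeks (the synopsis projects about six months) and about 16 days from plug insertion to Visit 7. The number in follow-up is then (75/20) × (16/7) = 8.6, or (75/26) × (16/7) = 6.6. So about 7 to 9 of the 50 would be in follow-up and about 41 to 43 not yet randomised. Enrolment during data entry, verification and analysis lowers the number further; the documents do not state how long that takes.

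**3. How a known effect helps guessing (illustration only).** The prior chance of placebo under 2:1 allocation is 1/3. Section 2.1 gives Day 1 pain-free rates of about 80% on nepafenac 0.1% and 50% on vehicle.

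- P(placebo | pain) = (1/3 × 0.5)/(1/3 × 0.5 + 2/3 × 0.2) = 0.1667/0.3000 = 56%
- P(placebo | no pain) = (1/3 × 0.5)/(1/3 × 0.5 + 2/3 × 0.8) = 0.1667/0.7000 = 24%

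With the Day 14 rates for nepafenac 0.3% (86% vs 46%, 84% vs 38%), the chance of placebo given pain is 0.1800/0.2733 = 66% and 0.2067/0.3133 = 66%. These rates are already printed in the protocol, so a rater could make the same inference before any interim. The figures show the mechanism, not the increment due to disclosure.

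**4. How precisely an interim at 25 would show the effect.** Assume 17 active and 8 placebo, with true rates of 80% and 50%. SE = √(0.8 × 0.2/17 + 0.5 × 0.5/8) = √(0.0094 + 0.0313) = 0.20. The 95% interval around a 30-point difference is about −10 to +70 points.

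**5. Under the proposed change.** No subject would be rated by an Investigator who had seen the interim comparison under the plan, against a ceiling of 50. The sample size stays at 75.

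**The case against.** The strongest reply is that this is a Phase 2 pilot, individual codes stay masked, disclosure is optional, and Investigators already know from the protocol's own background that topical nepafenac beats vehicle. An interim on 25 subjects would add an imprecise estimate (step 4). Pain is the subject's own report against written descriptors, and cells are graded in count bands, which narrows the room for rater influence.

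Much of this stands, and it rules out several stronger readings that a reader might infer:

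- *That raters will learn the effect.* Section 10.4.7 only allows it, and Section 8.8 neither mentions the interim nor says that Investigators receive its tables.
- *That the guessing figures measure the harm.* They rest on prior-trial rates available to every Investigator from the start.
- *That two thirds of subjects will be affected.* 67% is a ceiling at the earliest permitted interim.
- *That rescue is unrestricted, or that one rater is compulsory.* Section 7.9.1 states rescue criteria and Section 7.9 treats use outside them as prohibited medication. Rater continuity is a recommendation.
- *That the plan shields the Medical Monitor but not the raters.* Sections 8.9 and 10.4.7 keep both masked to treatment in the same sense, and neither bars access to summary results.
- *That the bias has a known direction or is beyond examination.* The documents do not establish a direction. Ratings before and after the disclosure date could be compared, though with little power.

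What does not stand is that the pilot label makes the permission harmless. The study tests hypotheses at a two-sided 5% level, relies on masking as its stated bias control, and may support a move to Phase III. Earlier drop trials show what nepafenac can do; the interim would show what this plug appears to do. The protocol gives no reason why sites need that before the end.

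**Conclusion.** The point holds as a permitted and avoidable route to bias, not as a demonstrated bias. The current text allows aggregate interim efficacy results to reach the people who rate the primary and secondary endpoints, and nothing elsewhere withdraws that permission. Section 8.8 adds a second route by implication only.

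The exposure depends on when the interim is run, how fast subjects accrue and whether the permission is used: from none, if nothing is shared and Investigators see no efficacy evidence, up to the ceilings in the working. The effect on the treatment estimate cannot be quantified from the documents. The protocol should be changed before the interim takes place, because results once shared cannot be recalled and no masking assessment is planned that might reveal an effect on raters.

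**What to change.** In Section 10.4.7, replace the sharing sentence with: *Interim comparative results will be seen only by the statistician performing the analysis and sponsor decision-makers who have no role in rating subjects or in masked data review; sites will be told only whether enrolment continues or stops.*

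In Section 8.8, limit the Investigators' role to the safety limb, and leave the decisions on efficacy and lack of efficacy to the sponsor decision-makers and the statistician.

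The cost is a wording amendment to two sections. Sample size and visits do not change, and Investigators keep their input on safety. No new body is needed, since Section 8.8 already involves statisticians and sponsor representatives, but the sponsor must identify decision-makers who stay out of the subject and visit review described in Section 10.6.3. Two limits remain. Investigators do not see results until study end. A message to continue still hints at a positive trend, given the stated purpose of the interim, although it withholds the size and the pattern across endpoints.
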